Appendix 10: Appointment Reminder Card

Appendix 11: Completion Certificateions" Leaflet for
Mailing

TCU
1920-347
Approved on 2-8-2023
Expires on 1-24-2024

Summary

The purpose of the Substance Use and Health Risk Intervention (SUHRI) project is to adapt and test an integrated health risk-reduction and motivational enhancement intervention (a cloud-based app) for Juvenile Justice (JJ) youth that will ultimately be (after full testing through a subsequent large-scale RCT) a sustainable intervention implemented within a JJ supervision/case management context to teach and facilitate positive, prosocial, and expected behaviors. The intervention will use interactive graphical approaches to encourage introspection and problem identification, enhance self-regulation, improve analytical problem-solving skills, and promote healthy behaviors in two inter-related target areas: substance use and risky sex practices. App sessions will be self-directed (require minimal instruction/interaction assistance), and also include a service referral piece whereby youth are provided with additional resources for seeking services related to risky health behaviors and substance use.

This research will be carried out in two pilots: (1) Intervention Adaptation and Feasibility and (2) Protocol Feasibility. The specific aims of the project are to (a) examine intervention feasibility and acceptability (Pilot 1), (b) *test the feasibility of the study protocol (adherence, subject retention, instrumentation) with JJ-involved youth (Pilot 2).*

During Pilot 1, intervention content will be adapted from existing evidence-based interventions so that it is developmentally appropriate for the target population and suitable for a web-based format. During Pilot 2, a test of the intervention will yield data on intervention feasibility, acceptability, and impact on youth outcomes. Proximal outcomes include improvements in change mechanisms (e.g., problem recognition, decision making, intention to reduce personal risk) and service initiation (SU or STI-related services). Distal outcomes include reduction in risky behaviors, including substance use (self-report and urinalysis) and sexual health risk (self-reported risky sex practices). Successful completion of the aims will result in an intervention that is appropriate and feasible for use with JJ-involved youth.

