To ensure fidelity to the study protocol and to avoid any perceived coercion by JJ staff, TCU Institute of Behavioral Research (TCU/IBR) RAs will oversee intervention administration, including voluntary study enrollment and withdrawal if requested. Following our NIDA-funded JJ- TRIALS study protocol, NO participant information (youth participation, youth assessment responses, choices/responses selected during the intervention, completion of sessions) will be shared with JJ staff; only aggregate information will be shared with JJ leadership.

11. Location:

All intervention and assessments sessions will take place either online using a platform such as Zoom, in-person at a Tarrant County Juvenile Services office or another public place, or via a tablet hand-off in an agreed upon public place. All TCU rules and regulations regarding COVID-19

protocols will be followed for in-person interactions including masking, hand-washing/sanitizing, social distancing when able, and sanitizing of all equipment.

12. Subject Population:

Participants will include juvenile justice-involved youth on probation within at least 1 local juvenile probation department (Tarrant County, currently). The Tarrant County Board (TCJS) has granted preliminary approval to submit appropriate requests to TJJD to move forward with planning this study.

We expect to recruit approximately 60 youth who range in age from 14 to 18 years old.

Inclusion Criteria: Youth ages 14-18 on community supervision are eligible if they have 1 or more indicator(s) of substance use, are English-speaking, and have no indication of current suicide risk or severe cognitive impairment/thought disorders. Youth's parent/legal guardian may be Spanish-speaking. Upon approval of the parental consent document, it will be translated into Spanish and submitted to the IRB for approval.

Exclusion criteria: Youth who are on TJJD (state) supervision rather than county supervision are not eligible to participate. In addition, youth who are currently suicidal, homicidal, or otherwise severely impaired (e.g., active psychotic symptoms) such as severe cognitive impairment or thought disorders are not eligible. Youth younger than 14 and youth 19 or older are likewise not eligible.

13. Recruitment Procedure:

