To request corroborating data from the local JJ department as well as the Texas Department of Juvenile Justice (TJJD), the research team will request that the TCJS research director provide the TJJD-based identification number (PID) for consenting participants as well as demographic, substance screening and assessment, and relevant service attendance information. These data will be shared via a spreadsheet available to the director of research and the research team via Box.com – a secure file-sharing platform. The research team will provide the PID numbers along with headquarters county ID to the TJJD data team via spreadsheet in a Box folder in return for state-level data specific to the youth's substance use screening and assessments as well as offense, background, and service-seeking data. The TJJD research proposal submitted in September 2020 can be found in Appendix 9. be found in Appendix 9.

Intervention

The youth will receive 4 sessions of the interactive, cloud-based intervention administered via a tablet we give them. Each session of the intervention will focus on one of topics associated with drug use and risky sex practices. The final session will include an integrated module ensuring that youth process through a scenario that examines how drug use and risky sex behaviors are related. The youth will complete the final WORK-IT scenario within the app with processing questions (see Appendix 5.7) to work through this integrated scenario and also a quiz-like activity on Kahoot to learn more about local resources for substance use and sexual health.

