The proposed studies will follow established procedures based on our previous NIDA studies outlining Common Adverse Events (AEs) and Serious Adverse Events (SAEs) for substance abuse research. Adverse events are defined as any event or outcome that has resulted in harm to the participant, has affected the participant detrimentally, has worsened as a result of participation in the study, or has resulted in increased risk to the participant or others whether or not the risk actually results in harm.

SUHRI DATA AND SAFETY MONITORING PLAN

Our Data and Safety Monitoring Plan (DSMP) will be consistent with plans and procedures we have used in our other federally-funded research projects. These include installation of an 800 (toll free) number in the US for research sites to use for reporting adverse events (AEs) to the PI, Co-Is, and research team. The PI will serve as liaison with our university IRB and will monitor and report problems and AEs as directed. Specific plans and reporting formats will be developed and reviewed and approved by the IRB prior to the onset of any research involving the proposed pilot studies. Reporting forms will be developed and participating staff will be trained to identify and report problems and AEs. The agenda for the weekly data management team meetings also will include problem and adverse events reports, and all reports will be immediately forwarded to the PI. The PI will assume overall responsibility for assuring the safety of study participants and will assure that the TCU IRB is informed of all safety issues.

Definitions of Adverse and Serious Adverse Events

The proposed studies will follow established procedures based on our previous NIDA studies outlining Common Adverse Events (AEs) and Serious Adverse Events (SAEs) for substance abuse research. Adverse events are defined as any event or outcome that has resulted in harm to the participant, has affected the participant detrimentally, has worsened as a result of participation in the study, or has resulted in increased risk to the participant or others whether or not the risk actually results in harm.

Specific Adverse Events (as observed or reported by participants or staff) include:

Violation of confidentiality (e.g., release of participant data to a non-authorized 3rd party)

Institutionalization in residential treatment or substance use rehabilitation

Probation revocation, re-arrest, reincarceration (e.g., jail, prison, juvenile detention)

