Implementation feasibility measures will be recorded, summarized, and reviewed monthly by the PI and team in order to inform real-time protocol adjustments (e.g., changes in recruiting practices if target numbers are not reached). Once the targeted youth recruitment goal has been achieved, psychometric properties of baseline measures will be conducted (means, SD, coefficient alpha, exploratory/confirmatory factor analysis). Because the design calls for repeated measures at baseline, month 1, and month 3, measures will not be revised between administration points.

However, psychometrics (conducted on data from all time points) will be used to inform modifications prior to a full-scale R01 RCT and reliability of scales for use in exploratory analyses of intervention efficacy.

Baseline characteristics will be included as covariates in analyses. The distal outcome will be the percent of study subjects who use drugs (self-report, corroborated with positive urine test) at follow-up (1- and 3-months). All study participants (regardless of study retention) will be included in analyses (i.e., an intent-to-treat approach; ITT). Baseline variables that directly relate to our aims (e.g., drug use, risky sex practices) will be evaluated for use as covariates. Abstinence at each

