follow-up time point will be compared using chi square test. Our proximal outcomes will include putative measures (e.g., problem recognition, decision making, intention to reduce personal risk) and receipt of SU services (dichotomous measure from youth records). Because proportions of females and their SU rates are generally lower among JJ youth compared to males,⁶ and males/females may respond differently to MEC interventions,¹⁶ we will explore sex (as a biological variable) differences in SU, risky sex practices, and exploratory outcomes using univariate analyses (e.g., chi square, t-tests, ANOVA). We will also explore potential racial/ethnic disparities in order to more fully inform whether cultural modifications are needed for a subsequent application. A log rank test will be used to assess intervention dropout. Participants who withdraw consent or are lost to follow up will be missing on outcome measures. To address this, stochastic multiple-imputation will be attempted, which will provide maximum likelihood estimates, account for uncertainty in missing values, and provide unbiased estimates of the treatment effect if data are missing at random. Effect sizes will be used to calculate sample sizes needed for the larger R01. Calculations will include samples needed to assess intervention feasibility across sex and race/ethnicity subgroups.

21. Check List for the Items That Need to be Submitted:

a. Protocol	
b. Consent document	
c. HIPAA form if applicable	
d. Protecting Human Research Participants Training certificate for each investigator	
e. Recruitment flyers, letters, ads, etc.	
f. Questionnaires or other documents utilized in screening and data collection	

Principal Investigator Assurance

22. By signing below, I certify to the following:

- The project described herein will be conducted in accordance with applicable TCU policies and procedures, as determined by the IRB of record. All Human Subject Research projects occurring at TCU must be conducted in compliance with the Office of Human Protection ("OHRP") regulations at 45 CFR 46 and all other applicable federal and state laws and regulations (collectively "Applicable Law")
- I have a working knowledge of Applicable Law

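### Pilot 2 is meant to test adherence and retention, but its only named dropout analysis is a log-rank test with no groups to compare, which cannot return a completion or retention rate

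*Combined protocol and SAP*

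**What the plan says.** The Summary gives the aim of Pilot 2 as to "test the feasibility of the study protocol (adherence, subject retention, instrumentation) with JJ-involved youth". Section 12 sets the size: "We expect to recruit approximately 60 youth who range in age from 14 to 18 years old". No precision target, power or expected retention accompanies that number.

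Section 15 (Intervention) describes a single course of treatment: "The youth will receive 4 sessions of the interactive, cloud-based intervention administered via a tablet we give them". No randomisation, allocation ratio or control condition is described for Pilot 2.

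Section 20 covers adherence and retention in two places. First, "Implementation feasibility measures will be recorded, summarized, and reviewed monthly by the PI and team", with the stated purpose of adjusting the protocol in real time; the measures are not listed. Second, "A log rank test will be used to assess intervention dropout". The groups, the dropout event, the time origin and the censoring rule are not given. Instrumentation has its own psychometric analysis in the same section.

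The safety plan in section 16 foresees events that could end participation. They include "Probation revocation, re-arrest, reincarceration (e.g., jail, prison, juvenile detention", residential treatment, and discontinuation by the investigators after a serious adverse event. Section 15 adds a fixed project end on 8/31/23. Section 20 mentions only consent withdrawal and loss to follow-up, and only as reasons for imputing outcomes.

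**The concern.** The question Pilot 2 was set up to answer has the thinnest analysis in section 20. Drug use, a distal outcome, has a defined percentage, two time points, an analysis population, a test and a plan for missing data. Adherence and retention have a test that produces a p-value for a difference between unnamed groups.

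Section 20 says the pilot will feed the design of an R01 trial. Planning that trial needs the proportion of enrolled youth who complete the sessions, the proportion who give follow-up data, and how many of the losses the study could have influenced. A youth who loses interest and a youth placed in detention both stop attending. The first bears on acceptability. The second bears on setting and on how far the next sample must be inflated. If section 20 is followed as written, none of these figures is specified as a result.

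**Working it through.** The plan states no retention rate, bar or sample-size derivation, so there is no figure of its own to reproduce. All rates below are assumptions; only n = 60 and the dates come from the protocol.

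**1. What the log-rank test can return.** It compares observed with expected events across two or more groups. With one arm there is no second curve, so no choice of event definition makes it yield a completion rate.

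**2. If subgroups were intended.** Section 20 explores differences by sex, so take sex as the grouping, with two-sided alpha 0.05. Events needed for hazard ratio 2 at 80% power:
- Schoenfeld, 1:1: (1.96 + 0.842)² / [0.25 × (ln 2)²] = 65.3, so 66.
- Schoenfeld, 25:75: the same numerator over 0.1875 × (ln 2)², so 88.
- Freedman, 1:1: (1.96 + 0.842)² × [(2 + 1)/(2 − 1)]² = 70.6, so 71.

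Each exceeds the 60 youth expected. With 12 to 24 dropouts and 20% to 50% of youth in the smaller group, power for hazard ratio 2 is 16% to 40%, and the ratio detectable with 80% power is 3.1 to 7.6.

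**3. What a proportion would give at n = 60.** Clopper-Pearson limits are the 2.5% point of Beta(x, n − x + 1) and the 97.5% point of Beta(x + 1, n − x).

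| Completing (assumed) | Rate | Exact 95% CI |
|---|---|---|
| 36/60 | 60% | 46.5% to 72.4% |
| 42/60 | 70% | 56.8% to 81.2% |
| 48/60 | 80% | 67.7% to 89.2% |
| 54/60 | 90% | 79.5% to 96.2% |

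**4. Why the reason for stopping matters.** Hold youth who stop by choice at 9 of 60 (15%). With 6 others removed for other reasons, completion is (60 − 9 − 6)/60 = 75%. With 12 removed it is (60 − 9 − 12)/60 = 65%. The overall rate moves by 10 points while stopping by choice does not change.

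**5. Where project end acts.** Referrals close on 05/31/2023, 92 days before 8/31/23. Suppose a youth is referred and consented on 31 May, starts a week later (7 June) and takes about 30 days over the sessions.
- Sessions finish about 7 July, inside the window.
- Three months (91 days) after a baseline on 7 June is 6 September, outside it. A baseline taken on 31 May itself would give 30 August, just inside.
- Three months after the last session is 6 October, outside it.

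Under the same assumptions, the latest consent date that fits is about 25 May on the post-baseline clock and about 25 April on the post-intervention clock. Section 15 uses both clocks: Procedures counts the 3-month assessment from the end of the intervention, Assessment counts it from baseline. Project end therefore cuts month-3 retention for late entrants and barely touches session completion.

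**The case against.** Three points on the other side have force.

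First, feasibility is not left to the log-rank test alone. Monthly summaries are planned, instrumentation is analysed, and the safety plan calls for a report that includes participant status. Detention, placement and serious adverse events are recorded as safety events. Much of the raw information will exist. This stands, and it is why the remedy is cheap; but no final adherence or retention estimate is specified from that information.

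Second, a reader might infer that the plan counts detained, placed or withdrawn youth as dropouts. It does not say so. The event and the censoring are undefined, so combining the causes is possible, not prescribed. Nor does the safety plan say that those events end sessions.

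Third, a reader might infer that the pilot cannot find the protocol infeasible, pointing to the Summary: "Successful completion of the aims will result in an intervention that is appropriate and feasible for use with JJ-involved youth". That sentence is conditional summary prose and not a decision rule. Having no pre-set criterion does not stop the team from judging the rates poor.

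The safety plan also speaks of comparing adverse events between study groups, and section 20 mentions a treatment effect, which might suggest a second arm. No such arm is set up anywhere in the Pilot 2 procedures.

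**Conclusion.** The point holds in this form: section 20 names a between-group test for a single-arm feasibility question, leaves dropout undefined, and specifies neither a final completion or retention rate nor a breakdown by reason. The conclusion about the test rests on Pilot 2 being single-arm, as the procedures describe. A subgroup log-rank test would not rescue it, since hazard ratio 2 needs 66 or more dropouts among about 60 youth. A simple proportion would be informative: at an assumed 70% completion the exact interval runs from 57% to 81%.

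The size of any distortion from pooling reasons for stopping cannot be taken from the documents; the 10-point shift above follows wholly from the assumed counts. This should be corrected before the data are summarised.

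**What to change.** Replace the log-rank sentence in section 20 with text to this effect:

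- Report the number and proportion of all enrolled youth completing each of the four sessions, and the proportions giving month-1 and month-3 assessments, each with an exact 95% CI.
- Record one reason for each stop: youth or family choice, detention or placement, safety withdrawal, or project end. Report cumulative incidence by session for each class.
- Also show month-3 retention among youth whose month-3 date falls on or before 8/31/23.

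Before this is applied, reconcile the post-intervention and post-baseline timing of the follow-up assessments in section 15, and the project end date, which section 13 still gives as 8/31/22. State when a youth counts as enrolled, because section 14 allows assent to wait until the first session.

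A progression criterion is optional. If the sponsor wants one, it should be fixed before the data are summarised. If two criteria must both be met, state their joint performance. As an illustration only, a bar of at least 44 of 60 is passed with probability 0.92 at a true rate of 80%. Passing two such bars has probability 0.923 × 0.923 = 0.85 if they are independent, and at most 0.92.

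The cost is one reason-for-stopping field and a little more analysis, with no extra visits or participants.

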Following assent and assessment the youth will receive a tablet to use during the study. The RA will walk through a tutorial with youth to ensure they learn how to use the tablet. The youth will then have the first intervention session with the RA. The RA will complete administrative procedures to ensure the youth is presented with the correct modules for the session, and the youth will complete the session independently with the RA available to answer questions. Once the youth completes the session, they will complete an end of session evaluation (using Qualtrics), and the RA will transition the youth out of the session and schedule the next session or the follow-up assessment (following the 4th session of the intervention).

The first intervention session will occur approximately a week after the consent/assent meeting, and each session will occur a week to several weeks apart (spanning across approximately 1 month).

Following the last session, the youth will be scheduled to complete a 1-month assessment either in-person or online with the RA. The youth will receive 2 reminder e-mails and text messages leading up to the assessment appointment. The youth will also complete a 3- month post- intervention assessment proctored virtually or in-person by the RA. The youth will also receive 3 reminder e-mails and text messages leading up to the final assessment. Reminder e-mails will come from the e-mail address [contact] with the subject line "SUHRI Reminder" directly to the youth's personal e-mail address to reduce the chance that another individual will see the e-mails. No reference to a research project will be made in the text.

Each follow-up assessment will last approximately 60 minutes, with intervention sessions lasting approximately 60 – 90 minutes each.

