Probable: SAE is likely related to the intervention Possible:
SAE may be related to the intervention Unlikely: SAE is
doubtfully related to the intervention Unrelated: SAE is
clearly not related to the intervention

Participants' descriptions of adverse events (incident reports) will be grouped in a reasonable way, counted, and compared by study groups. A designation of "more-common" will be given to events occurring at an incidence of at least 5% in participants assigned to an intervention group, and for which the incidence is at least twice that observed in a comparison group. Staff will be trained to carefully observe participants' reactions to the study protocol and to take appropriate action including support, discontinuance, or referral to additional counseling services, if necessary. Based on previous experience and the current use of these TCU materials with other IRB research projects we have found that such occurrences are rare.

Reporting Timeline

SAEs will be reported to the PI within 24 hours of detection. Within 3 business days, the PI will send a full report on the SAE, including the action taken with regard to continued study participation to the IRB. Non-serious AEs or adverse effects that lead to subject removal from the protocol will be reported to the IRB within 7 business days. The PI will maintain a record of the SAEs, which can be provided to the IRB electronically. The outcome of SAEs also will be reported to NIDA in annual reports. A summary of the SAEs and AEs that occurred during the previous year will be included in the annual progress report to NIDA.

17. Potential Benefits:

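### The adverse-event rule needs a comparison group that the Pilot 2 procedures do not describe, and for the same reason the pilot's effect sizes cannot supply the between-arm difference the R01 trial needs

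*Combined protocol and SAP*

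**What the plan says.** The Summary places the definitive test of the app later, "after full testing through a subsequent large-scale RCT". Section 20 confirms the design of that next study: psychometric results "will be used to inform modifications prior to a full-scale R01 RCT". It then gives the pilot a role in sizing it: "Effect sizes will be used to calculate sample sizes needed for the larger R01". No outcome, time point, contrast or metric is named for those effect sizes. The next sentence extends the calculation to sex and race/ethnicity subgroups.

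For Pilot 2 itself, Section 12 expects about 60 youth. Section 15 takes each of them through consent, assent, baseline assessment and a tablet, and then: "The youth will then have the first intervention session with the RA". Four sessions follow, with assessments at baseline, 1 month and 3 months. These sections mention no randomisation, allocation or control condition.

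The monitoring plan in Section 16 (Approach for Reviewing Problems) is written differently. Incident reports "will be grouped in a reasonable way, counted, and compared by study groups". The more-common label sets a 5% floor and is defined by reference to "participants assigned to an intervention group, and for which the incidence is at least twice that observed in a comparison group".

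Two tests in Section 20 name no groups. Abstinence at each "follow-up time point will be compared using chi square test", and "A log rank test will be used to assess intervention dropout".

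**The concern.** There are two linked problems. First, the safety rule divides by an incidence that the described study will not produce. Staff following the plan could count events but could not apply the label.

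Second, a randomised trial is sized on the difference between its arms. If Pilot 2 has a single treated cohort, the only intervention effect it can yield is the change from baseline to follow-up. That change combines the effect of the app with whatever would have happened under ordinary supervision. Using it as the between-arm difference makes the R01 too small if untreated youth would also have improved, and too large if they would have worsened. The documents give no figure for either.

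**Working it through.** **Design, set side by side**

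| Place | What it implies |
|---|---|
| Section 12 | one group of about 60 youth |
| Section 15 | each youth gets four sessions; three assessments; no allocation step |
| Section 16, more-common rule | an intervention group and a comparison group |
| Section 20, chi-square and log-rank tests | groups not named |
| Section 20, sizing sentence | effect sizes of an unnamed kind, for a randomised trial |

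The first half of the more-common rule can be checked in one cohort: 5% of 60 is 3 youth. The second half needs a ratio of two incidences, and with one cohort the denominator does not exist.

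**Is there a figure to reproduce?** No. The documents give no alpha, power, expected use rate, SD or loss to follow-up for either study, and no R01 sample size. What follows is an illustration. Only the pilot size of about 60 and the outcome come from the documents. Section 20 defines the distal outcome as the percentage of youth using drugs at 1 and 3 months.

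**Assumptions:** two-sided 5%, 80% power, 1:1 allocation in the R01, 60% using drugs at follow-up with the intervention (pT), and a control rate (pC) of 80%, 75%, 70% or 65%.

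Formula for n per arm, with p̄ = (pC + pT)/2:

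n = [1.960·√(2p̄(1−p̄)) + 0.8416·√(pC(1−pC) + pT(1−pT))]² / (pC − pT)²

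For pC = 0.80: p̄ = 0.70, and n = [1.960·√0.42 + 0.8416·√0.40]² / 0.20² = (1.270 + 0.532)² / 0.04 = 81.2, so 82.

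| Control rate | Difference | n per arm |
|---|---|---|
| 80% | 20 points | 82 |
| 75% | 15 points | 152 |
| 70% | 10 points | 356 |
| 65% | 5 points | 1471 |

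**How a before-after effect would enter.** Suppose 80% used drugs at baseline (assumed) and 60% at follow-up. Treating the 20-point fall as the between-arm difference gives 82 per arm. If untreated youth would have fallen to 70%, the true difference is 10 points. Power with 82 per arm is then Φ[(0.10·√82 − 1.960·√0.455)/√0.45] = Φ(−0.62), or about 27%.

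**What about 60 youth can estimate.** One follow-up rate near 60% has a 95% half-width of 1.96·√(0.6·0.4/60) = 12.4 points, before any loss to follow-up. If there were a comparator with 30 youth per arm (assumed) and rates near 50%, the difference would have a half-width of 1.96·√(0.25/30 + 0.25/30) = 25.3 points. That removes the before-after bias but leaves a very imprecise difference.

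**The case against.** **The group wording may be carried over.** Section 16 says the monitoring plan follows those used in the investigators' other federally funded projects, and its opening is printed twice. That makes leftover text plausible, though the plan does not say so. If it is leftover, the correction is to wording rather than design, but the rule still cannot be applied as it stands. The appendices and some pages of the document were also not available for this review, so a comparator described there cannot be excluded. The procedures describe none.

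**The plan never says a before-after change will size the R01.** This is correct. A reader might infer that the investigators have chosen that effect size, or that the R01 is already mis-sized. The documents support neither inference: Section 20 names no contrast, and no R01 sample size exists.

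**The unnamed tests fit a single arm.** A reader might take the chi-square and log-rank tests as further evidence of a hidden second arm. They are not. Section 20 plans comparisons by sex and by race/ethnicity, and abstinence could be contrasted over time. These tests are under-specified, not contradictory. Only the Section 16 rule clearly conflicts with the procedures.

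**This is a feasibility pilot.** That stands. Its stated aim is protocol feasibility, and Section 20 calls the efficacy analyses exploratory. But Section 20 itself gives the pilot its role in sizing the R01, so the basis for that should be sound.

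**Conclusion.** The point holds in two parts. On the available text, the Section 16 rule conflicts with the procedures and cannot be computed. For the same reason, the Section 20 sizing sentence asks the pilot for a between-arm difference that one treated cohort cannot give.

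The second part is conditional. It matters only if change over time is used to size the R01, and the harm would fall on that later trial. Adherence, retention and instrumentation results from Pilot 2 are unaffected.

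The possible size is large. In the illustration the R01 requirement runs from 82 to 1471 per arm as the control rate moves from 80% to 65% with the intervention rate fixed at 60%. Those rates, the 5% level and the 80% power are all assumptions, so the figures show sensitivity and do not forecast the R01. The direction of any error is unknown. The plan should be changed, but this does not undermine the pilot.

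**What to change.** 1. **Reconcile Section 16 with Sections 12 to 15.** If Pilot 2 is single-arm, say so and replace the comparison-group rule with adverse-event counts and incidences with 95% confidence intervals. If a comparator exists, describe it in the procedures.
2. **Name the contrasts in Section 20.** State whether the chi-square and log-rank tests compare time points, sexes, racial/ethnic groups or arms.
3. **If single-arm, replace the sizing sentence** with text to this effect: *The R01 will be sized on a justified between-arm difference, with a sensitivity range for the control-arm rate. Pilot 2 will supply the follow-up use rate, SDs, within-youth correlation, session completion and 1- and 3-month retention, each with a 95% confidence interval. Before-after changes will be descriptive. Subgroup sizing will use the same basis.*
4. **If a comparator exists,** report the pilot between-arm estimate with its 95% confidence interval and take its imprecision into account when sizing the R01.

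The single-arm route costs a few sentences in Sections 16 and 20 and changes nothing for participants or pilot data. If a comparator is intended, the procedures and consent documents would also have to describe it. The downside of the single-arm route is that the planned R01 may turn out larger.
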